6 DOSING DELAYS/DOSE MODIFICATIONS

If patients drop below 20 kg during SYLATRON treatment, they can have SYLATRON held for up to 3 weeks for increasing nutrition. If they can gain weight and return to \geq 20 kg, they could restart SYLATRON and not make up lost weeks. This could happen twice before being removed from study.

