5.3.2 Off Treatment Criteria

At the discontinuation of treatment, the "Off Treatment Date" is to be recorded in the eCRF and is to be consistent with the reason given for going off treatment. The "Last Treatment Date" is defined as the last date that the patient received protocol based therapy. Date of "off treatment" must be the greatest of the date of last treatment, date of procedure, date of patient assessment, notification of patient/family decision, or decision made by the physician that resulted in the patient being taken off protocol treatment. The reason for discontinuation of treatment must be documented by the attending investigator in the medical record and recorded in the eCRF.

- Disease progression as defined in Section 11.1.3
- Development of a medical or psychiatric illness that in the investigator's judgment renders the patient incapable of further therapy on this protocol.
- Unacceptable toxicity as outlined in sections 6.
- Patient, parent or legal guardian refuses further treatment on this protocol
- Pregnancy or breastfeeding
- Subject is unable to complete the study evaluations/visits
- Patients who develop significant depression and/or suicidal ideations will be taken off treatment.

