5.4 Off Treatment Duration of Follow Up

Patients who are off protocol therapy must be followed until an "Off Study Criterion" is met (see section 5.6).

- 5.4.1 Patients who have had progression/recurrence will be followed for 30 days after the last dose of SYLATRON or until the resolution of all SYLATRON related toxicities, whichever is longer.
- 5.4.2 Patients who discontinue for reasons other than progression/recurrence of disease should continue to be followed for progression/recurrence, i.e. until they meet the Off Study criteria (below). Follow-up data will be required.
- 5.4.3 Patients removed from study for unacceptable adverse event(s) will be followed until resolution or stabilization of the adverse event and they meet one of the Off Study criteria (below).

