5.5 Criteria for Removal from Study

The date and reason for the subject coming off study must be documented in the eCRF and the Operations, Biostatistics and Data Management Core must be notified according to standard reporting guidelines (see Section 7 and the Required Data and Timetable Submission form located on the PBTC-039 protocol and resources webpage).

- Subject determined to be ineligible.
- Parent, subject, or guardian withdraws consent for continued participation.
- Subject death while on study. The IRB, Study Chair and OBDMC must be notified as per Section 7.
- Subject has completed all trial-specified evaluations and follow-up.

• Subject has started another therapy or experienced disease progression (section 11.1.3).

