5.5.1 Off-Study Data Submission Schedule

No data will be collected documenting treatment or reporting events or disease status that occur subsequent to the official "off study" date with the exception of adverse events with an attribution of possible, probable, or definite that occur after the "off study" date (per protocol Section 7).

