6.1 Constitutional Symptoms

Every attempt should be made not to stop the drug for constitutional symptoms during the first three weeks, since these symptoms usually improve. Patients with persistent (i.e. lasting > 48 hours) grade 2 or higher constitutional symptoms occurring after the fourth dose should have their dose reduced to 0.6 mcg/kg/week. If symptoms do not improve after 3 weeks of the reduced dose, patients may have their dose reduced to 0.3 mcg/kg/week. If symptoms do not improve after 3 weeks of the second dose reduction, the patient should be taken off treatment.

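### The weight rule in Section 6 takes a child off study rather than off protocol therapy, at odds with the follow-up that Section 5.4.2 requires

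*Combined protocol and SAP*

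**What the plan says.** The opening paragraph of Section 6 covers children who fall below 20 kg during treatment. The drug may be held for up to 3 weeks while nutrition is improved, and it restarts if weight recovers. The paragraph then limits the number of holds: "This could happen twice before being removed from study".

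The protocol separates leaving treatment from leaving the study:

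- **Leaving treatment.** Section 5.3.2 lists seven reasons, one of which is "Unacceptable toxicity as outlined in sections 6". Low weight is not named.
- **Follow-up after treatment.** The lead sentence of 5.4 keeps patients in follow-up until an off-study criterion "is met (see section 5.6"). Under 5.4.2, "Patients who discontinue for reasons other than progression/recurrence of disease should continue to be followed for progression/recurrence", and follow-up data are required.
- **Leaving the study.** Section 5.5 lists five criteria: ineligibility, withdrawn consent, death, completion ("Subject has completed all trial-specified evaluations and follow-up"), and progression or another therapy. Low weight is not among them.
- **Consequence of leaving the study.** Section 5.5.1 states: "No data will be collected documenting treatment or reporting events or disease status that occur subsequent to the official" off-study date. The only exception is for adverse events attributed to treatment.

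The analysis plan in 13.3 estimates PFS by Kaplan-Meier in each stratum, with patients still at risk censored at last contact.

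**The concern.** A child who can no longer be dosed because of weight has not progressed and has not withdrawn. Such a patient should leave the drug and stay under observation, which is what 5.4.2 provides. The weight rule instead uses the term that the protocol reserves, in the heading of 5.5, for the end of participation.

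A site that takes the phrase at face value would record an off-study date, and 5.5.1 would then end collection of disease status. The child's later progression or progression-free time would be lost to a secondary endpoint. The censoring might also not be independent of outcome, because the weight loss may be caused by the drug: Section 2.2.1 lists anorexia and weight loss among the toxicities of the earlier interferon study, and 7.1.1 lists loss of appetite as common. Sites that read the phrase differently would handle the same event differently.

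**Working it through.** No stated figure has to be reproduced. The check is a comparison of texts with two small pieces of arithmetic.

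**1. Is 20 kg a dosing limit?** Section 3.1.10 ties the minimum weight to the smallest injectable volume, 0.05 ml (20 mcg). Appendix C gives volume = weight × dose ÷ vial strength. At 20 kg and 1 mcg/kg with 400 mcg/ml, this is 20 × 1 ÷ 400 = 0.05 ml. The floor is therefore the weight at which the full dose equals the minimum volume. That is a reason to stop dosing and gives no reason to stop observing.

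**2. How are the other permanent stops in Section 6 worded?**

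| Place | Permanent stops | What is stopped |
|---|---|---|
| 6.1 | 1 | treatment ("the patient should be taken off treatment") |
| 6.3, grade 4, cardiopulmonary and grade 3 | 3 | protocol treatment (1), protocol therapy (2) |
| 6.3, persistent grade 2 | 2 | protocol therapy |
| 6.4 | 2 | protocol therapy (1), the drug, permanently (1) |
| Total | 8 | none is from the study |

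The first stop in 6.3 has two triggers. Counting by trigger gives nine, and still none is from the study. Outside Section 6, the rule in 5.2 for a course delayed more than 21 days also ends protocol therapy only.

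**3. Is weight listed as a reason anywhere?** The lists in 5.3.2 and 5.5 hold 7 + 5 = 12 reasons. Low weight is named in none of them.

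**4. What follows from each reading?**

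- *Off study:* 5.5.1 applies, disease status is no longer collected, and PFS is censored at removal.
- *Off protocol therapy:* 5.4.2 applies, and the child is followed until an off-study criterion in 5.5 is met.

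**5. How large is it per child?** Using the planned evaluable numbers in 13.3, one PFS time is 1/28 = 3.6% of Stratum 1 or 1/19 = 5.3% of Stratum 2. These are shares per child, not estimates of impact. The documents do not say how many children will be near 20 kg, so the number affected cannot be calculated and may be zero.

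**The case against.** The strongest reply is that this is loose drafting that the rest of the protocol already corrects. Section 5.4.3 speaks of patients removed from study for unacceptable adverse events, yet says that they "will be followed until resolution or stabilization of the adverse event and they meet one of the Off Study criteria (below"). The phrase is thus used elsewhere for patients who are still followed. Sections 5.4 and 5.4.2 are the dedicated follow-up rules, and 5.5 is the dedicated off-study list. Harm requires a site to put one phrase in a dosing section above all of these. Much of this stands: the intent is probably off treatment. It does not remove the point, because 5.4.3 concerns adverse events and Section 6 does not classify low weight as one, so the site has to infer the intent.

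A second reply is that weight loss on the drug can already come under the toxicity reason in 5.3.2. That is fair, and it makes a separate entry there optional.

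A third reply is that a child under 20 kg becomes ineligible, which is an off-study criterion. This fails. Section 3.1.10 and Appendix C describe entry, and 5.2 re-applies only the laboratory limits of 3.1.11.

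A fourth reply is that little would be gained. Removal requires repeated falls below 20 kg with recovery between them. PFS is secondary and descriptive, with no test attached. Neither 9.3.3 nor the study calendar schedules scans after treatment ends. This stands and limits the size of the point.

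A reader might also infer a cost to the Stratum 1 primary endpoint or its power. The documents do not support that. Scoring an unevaluated child as a failure comes from the note to the study calendar and from 13.4.1, which apply to patients removed from treatment as well. Section 13.3 also bases the design on completing 9 courses without an event, which a child stopped earlier has not done under either label. No removal rate is given from which a loss of power could be calculated.

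**Conclusion.** The point holds as a minor wording inconsistency with an operational consequence. The weight rule is the only permanent stop in Section 6 worded as leaving the study, and taken literally it conflicts with 5.4.2 and brings 5.5.1 into play for a child who has not progressed. The effect is at most a few PFS times censored early, possibly none, and it arises only if a site follows the literal wording. The sample sizes, decision rules, type I error and power are untouched. Confidence is high on the wording. How often the event occurs and how sites would read the phrase are unknown.

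**What to change.** In the opening paragraph of Section 6, replace removal from study with removal from protocol therapy. Follow-up under 5.4.2 then applies as it does after any other non-progression stop.

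Two clerical items can be tidied at the same time. The pointer in the lead sentence of 5.4 should read 5.5, since 5.6 deals with concomitant medication. Low weight could also be named in 5.3.2.

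The 20 kg floor, the hold rule, the primary endpoints and the failure rule for unevaluated patients stay as they are. The cost is one phrase, plus one section number and one bullet if the tidying is done. In practice it means follow-up data from very few children, whose later disease status will partly reflect time off the drug.

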6.1 Constitutional Symptoms

Every attempt should be made not to stop the drug for constitutional symptoms during the first three weeks, since these symptoms usually improve. Patients with persistent (i.e. lasting > 48 hours) grade 2 or higher constitutional symptoms occurring after the fourth dose should have their dose reduced to 0.6 mcg/kg/week. If symptoms do not improve after 3 weeks of the reduced dose, patients may have their dose reduced to 0.3 mcg/kg/week. If symptoms do not improve after 3 weeks of the second dose reduction, the patient should be taken off treatment.

6.2 Transaminase Elevations

No delays or dose modifications should be made for grade 1-2 elevation of SGOT/SGPT. For grade 3-4 elevations, the dose modifications below should be followed.

6.3 Non-hematologic toxicity other than constitutional symptoms

- Subjects who experience a grade 4 non-hematologic toxicity, or subjects who experience grade 2 or higher cardiopulmonary toxicity that is at least possibly-related to SYLATRON should be removed from protocol treatment and should not restart the drug.
- The development of any other SYLATRON related grade 3 non-hematologic toxicity should result in immediate discontinuation of the drug. Following the discontinuation of the drug, patient should be monitored and may restart the drug if following conditions are met:

Subjects who develop grade 3 SYLATRON-related non-hematologic toxicity other than constitutional symptoms should have the drug withheld until the toxicity resolves to grade ≤1. If the toxicity resolves to Grade 1 or better within 3 weeks of discontinuation of SYLATRON, patients may restart therapy at 0.6 mcg/kg/week.

Toxicity that does not resolve within 3 weeks will require the subject to be removed from protocol therapy. If the toxicity recurs at the 0.6 mcg/kg/week dose, the dose should be decreased to 0.3 mcg/kg/week, provided toxicity has decreased to Grades 0-1 within 3 weeks of discontinuation of SYLATRON. Recurrent Grade 3 non-hematologic toxicity following two dose reductions will require the subject to be removed from protocol therapy. No subsequent dose escalations are permitted after dose reduction for non-hematologic toxicity.

Subjects who develop persistent (≥7 days) grade 2 non-hematologic SYLATRON related toxicities (other than constitutional symptoms and transaminase elevations) that are considered sufficiently medically significant or sufficiently intolerable by patients as to warrant treatment interruption and/or dose reduction should have SYLATRON withheld until the toxicity resolves to grade ≤ 1 . If the toxicity resolves to Grade 1 or better within 3 weeks of discontinuation of SYLATRON, patients may restart therapy at the same dose. Toxicity that does not resolve within 3 weeks will require the subject to be removed from protocol therapy. If the grade 2 toxicity recurs, the SYLATRON dose should be withheld again until the toxicity resolves to grade 1 or better, at which point the dose should be decreased to 0.6 mcg/kg/week, provided toxicity has decreased to Grades 0-1 within 3 weeks of discontinuation of SYLATRON. If the toxicity recurs at the 0.6 mcg/kg/week dose, the dose should be decreased to 0.3 mcg/kg/week, provided toxicity has decreased to Grades 0-1 within 3 weeks of discontinuation of SYLATRON. Recurrent Grade 2 non-hematologic toxicity following two dose reductions will require the subject to be removed from protocol therapy. No subsequent dose escalations are permitted after dose reduction for non-hematologic toxicity.

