6.4 Dose Modification for Hematologic Toxicity

Any subject who has an ANC $<1000/\mu L$ or platelet count $<100,000/\mu L$ should have the test repeated within 1 week (prior to the next dose of SYLATRON). The criteria for dose modification are as follows:

- Absolute neutrophil count (grade 4) <500/μL
- Platelets (grade 3) < 50,000/ μ L

Whenever a subject's blood count(s) drop below the criteria shown above, the SYLATRON will be held until the count(s) recover to Grades 0-1 and the dose will be reduced to 0.6 mcg/kg/week. Toxicity must recover to Grades 0-1 within 3 weeks of discontinuation of SYLATRON in order to allow re-initiation of treatment at the reduced dose. Toxicity that does not resolve within 3 weeks will require the subject to be removed from protocol therapy. Should the toxicity recur at the 0.6 mcg/kg/week dose level, a second dose reduction to 0.3 mcg/kg/week should be performed provided the toxicity has decreased to Grades 0-1 within 3 weeks of discontinuation of SYLATRON. If there is again recurrence of hematologic toxicity meeting the above requirements for dose reduction (i.e., following the second dose reduction) treatment with SYLATRON will be discontinued permanently. No subsequent dose escalations will be permitted after dose reduction for hematologic toxicity.

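### The grade 3 rule in 6.3 restarts at a fixed 0.6 mcg/kg/week, so a patient already at 0.6 for constitutional symptoms or blood counts restarts with no dose cut

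*Combined protocol and SAP*

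**What the plan says.** All patients start at 1 mcg/kg/week (section 5.1). Section 6 then has separate reduction rules by type of toxicity.

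- **6.1, constitutional symptoms.** Persistent grade 2 or higher symptoms after the fourth dose reduce the dose to 0.6. The next step, to 0.3, is tied to the reduced dose itself: "If symptoms do not improve after 3 weeks of the reduced dose". Failure to improve after that means off treatment.
- **6.3, related grade 3 non-hematologic toxicity other than constitutional symptoms.** The drug is held. If the toxicity reaches grade 1 or better within 3 weeks, "patients may restart therapy at 0.6 mcg/kg/week". The step to 0.3 is conditional: "If the toxicity recurs at the 0.6 mcg/kg/week dose". Recurrent grade 3 toxicity after two reductions means removal. The rule closes with "No subsequent dose escalations are permitted after dose reduction for non-hematologic toxicity".
- **6.3, persistent related grade 2 toxicity.** After the first hold, "patients may restart therapy at the same dose"; later recurrences step to 0.6 and then 0.3.
- **6.4, blood counts.** The drug is held until recovery and "the dose will be reduced to 0.6 mcg/kg/week". The second step reads "Should the toxicity recur at the 0.6 mcg/kg/week dose level", and a further recurrence ends treatment. It closes with "No subsequent dose escalations will be permitted after dose reduction for hematologic toxicity".

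No section says how to treat a first event of one type in a patient whose dose was already reduced for another type. Sections 5.2 and 5.3.2 add only a 21-day limit on delay and a pointer back to section 6.

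**The concern.** The 6.3 grade 3 rule and the first step of 6.4 read as if every patient were still at 1 mcg/kg/week. That fails once a patient has been reduced under a different subsection. The plan clearly intends a lower dose after a first related grade 3 non-hematologic event, yet for a patient already at 0.6 the only restart dose it names is 0.6.

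Two types of toxicity in one patient are plausible. Section 7.1.1 lists fever, chills and tiredness, and separately liver damage, each as affecting more than 20 in 100. The first group falls under 6.1; section 6.2 sends grade 3-4 transaminase elevations to the later rules. Treatment can run to 18 six-week courses.

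At stake is the dose given to a few patients after a serious toxicity, and uniform practice across sites. Different local readings would also feed the tables of dose reductions and toxicity discontinuations planned in the section 13.3 analysis plan.

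**Working it through.** The plan states no figure to reproduce here. The check follows the written rules for each current dose, separating a first event of that toxicity type from a recurrence of it.

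| Current dose | Event | 6.3 grade 3 rule | 6.4 rule |
|---|---|---|---|
| 1.0 | first | 0.6 | 0.6 |
| 0.6 | recurrence | 0.3 | 0.3 |
| 0.3 | recurrence | removed | stopped permanently |
| 0.6, for another reason | first of this type | 0.6 named: no cut | to be reduced, but the figure named is 0.6 |
| 0.3, for another reason | first of this type | 0.6 named, but escalation barred; resume or stop not stated | same |

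The first three rows work. The fourth is the gap, and the fifth is silence.

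**Size of the step**

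- First step on the ladder: 1 - 0.6/1.0 = 40%.
- Second step: 1 - 0.3/0.6 = 50%.
- First grade 3 non-hematologic event at 0.6, as written: 1 - 0.6/0.6 = 0%.

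**Where the gap does not reach**

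- The second step of 6.1 depends on time at the reduced dose, not on why the dose was reduced, so it works for anyone at 0.6.
- The persistent grade 2 rule can be read to give 0.3 when the toxicity recurs at 0.6. Its same-dose restart after a first event is a deliberate choice for a milder toxicity.

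**How many patients**

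The patients at risk of the 6.3 gap are those already at 0.6 for constitutional symptoms or counts. Section 2.2.3 describes 12 children treated with this agent at this dose for another disease. It names one reduction, for grade 3 transaminases, and one dose-limiting myoclonus. Both are 6.3 events, so neither belongs to the group at risk. The number named for constitutional symptoms or counts is 0 of 12. The exact two-sided 95% upper limit is 1 - 0.025^(1/12) = 26.5%. The documents give no rate for a second type of event after such a reduction, so no expected count follows.

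**Effect on the endpoints if the fix makes a patient stop sooner and turns a success into a failure**

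- Stratum 1, final analysis: 1/28 = 3.6 points.
- Stratum 1, futility look: 1/12 = 8.3 points.
- Stratum 2, first stage: 1/11 = 9.1 points.
- Stratum 2, final analysis: 1/19 = 5.3 points.

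**The case against.** The strongest reply is that 6.3 permits restart and does not require it. The drug is stopped first, recovery to grade 1 or better within 3 weeks is needed, and a recurrence at 0.6 leads to 0.3. Grade 4 non-hematologic toxicity, and related cardiopulmonary toxicity of grade 2 or higher, mean removal. Course-start laboratory criteria also apply. All of this stands, and it is why the point is minor. It does not close the gap: the discretion is over whether to restart, and 0.6 is the only dose named. A site that prefers 0.3 has no written authority for it.

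A second reply is that 6.4 speaks of a reduction and allows re-initiation only at the reduced dose, which points to a real cut. That also stands. A reader might infer that 6.4 orders an uncut dose, or that it offers nothing below 0.6 and no stopping rule at 0.3. The text does not support either reading. Its wording for a first count event at 0.6 is ambiguous, and for a recurrence it gives 0.3 and then permanent discontinuation.

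A reader might also infer that 6.3 would raise a patient from 0.3 to 0.6. The no-escalation sentences most naturally bar that. For a patient reduced only under 6.1, which has no such sentence, the bar rests on counting constitutional symptoms as non-hematologic toxicity, as the heading of 6.3 implies. What is missing is whether to resume at 0.3 or stop, and both are conservative.

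**Conclusion.** The point holds for one defined case: a first related grade 3 non-hematologic event in a patient already at 0.6 under 6.1 or 6.4. As written, the restart dose is the dose that preceded the event. Section 6.4 has a parallel ambiguity for a first count event in a patient at 0.6 for another reason, and no rule is stated for a first event of a new type at 0.3.

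The number affected is unknown and probably very small. It is tempting to scale up the 1 of 12 or 2 of 12 in section 2.2.3, or the 9 of 15 in section 2.2.1, to the 52 planned patients. The documents do not support that. The first two counts are not of patients reduced for constitutional symptoms or counts. The third comes from a daily non-pegylated product and mixes temporary stops with reductions.

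The conclusion rests on reading the dose figure in 6.3 literally and on the absence of a general step-down rule elsewhere. Confidence is medium. This is a minor safety-conduct correction; sample size, power and error rates are unaffected.

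**What to change.** In the grade 3 rule of 6.3, and for consistency in 6.4, replace the fixed 0.6 with: one dose level below the dose being received at the event (1.0 to 0.6 to 0.3). State that the bar on escalation covers every reduction in section 6, including 6.1. For a first event of a new type at 0.3, state a single rule: stopping follows the logic of the ladder, but resuming at 0.3 after recovery is also defensible. Leave the second step of 6.1 and the same-dose restart after a first persistent grade 2 event as they are.

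The cost is wording in two subsections, with no added visits, tests or patients. The downside is that a few patients with two types of toxicity reach 0.3 or stop sooner. Those who stop are still followed for progression under 5.4.2. In stratum 1, however, they may not complete the 9 courses on which the design is based (13.3), and in either stratum those removed and not evaluated for the primary outcome count as failures (13.4.1). Obtaining the 12-month MRI limits that loss in stratum 1. One failure weighs most at the interim looks, so the choice of rule at 0.3 deserves a deliberate decision.

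Whether reduced doses below the 20 mcg minimum injection may be given, and whether the Appendix C chart should show 0.6 and 0.3, are separate matters that this correction need not settle.
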